## 3C.7. Outcome Measures

**3C.7.1. Measure of Primary Outcome Variable: IID Lockout Events.** The primary outcome

measure will be frequency of IID lockout events from baseline to 9-month follow-up post-randomization, collected from the Santa Fe DWI program database for each first-time DWI offender participant. Marques, Voas and colleagues have demonstrated in a series of investigations that frequency of lockout events strongly predicts DWI recidivism over time, and as such, IID lockout events are an important and useful proxy measure for DWI recidivism. Given the length of time necessary to accumulate DWI recidivism data (average length of time varies across locales and can be between 2 and 8 years), IID lockout events provide a direct and accessible measure of DWI recidivism within the two-year project timeline.

**3C.7.2. Measures of Secondary Outcome Variables and Mediators.** Alcohol use by the DWI offender, a secondary outcome, will be assessed at baseline, 3-month follow-up, and 9-month follow-up with versions of the Form 90 adapted for online assessment for the CFMs (Form 90-ACS) and first-time DWI offenders (Form 90-AF). The Form 90 measures produce detailed quantity and frequency measure of alcohol use for the first-time offender that are validated by the CFM reports. Family functioning will be assessed at baseline, 3-month follow-up, and 9-month follow-up, as potential mediators of *B-SMART* effects, with DWI offenders and CFMs with three measures: (1) Family Environment Scale – Cohesion and Conflict subscales assesses offender and CFM perceptions of positive and negative family functioning; the two subscales selected are strongly associated with treatment outcome; (2) Family Communication Scale from FACES-IV assesses perception of quality of communication in the family; (3) Pleasant Events Schedule (adapted) assesses shared positive activities within a family. These three measures are also being used in the B-FIT study, allowing for comparison of outcomes across the two studies.

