## STATISTICAL ANALYSIS PLAN

### Sample Size Determination

The sample size for the randomized trial in the Phase II research is designed to provide sufficient information for Phase III commercialization. The sample size assumes the counts of interlocks are Poisson distributed. We have assumed 4 interlocks over 9 months in the control arm or a rate of 0.44 per month for each DWI offender. In the *B-SMART mobile web app* group, we have assumed a reduction of 40% from 0.44, resulting in a rate of 0.27 per month. The null hypothesis is that the ratio of these two rates is 1.0 versus 0.6. Assuming a Type I error of 0.05 (2-sided), 90% power, sample size is only 27 DWI offenders per group. However, if the rate is higher up to 1 per month, the sample size required declines since the percent reductions yield wider absolute differences in the rates. We also are keen to know the reductions achievable with the *B-SMART* group, so we evaluated the sample size with regards to other effect sizes. In a Cochrane meta-analysis reported the impact of IIDs to reduce risk by 64%, but with a confidence interval that ranged from 76% to 37%. In the proposed trial, we have two treatment groups and may see less impact than that in the meta-analysis. Thus, a sample size of 119 DWI offenders per group will allow for 90% power with a comparison of 0.44 to 0.36 or approximately a 20% reduction in interlocks. We will adjust for an expected 15% attrition and this sample size also has sufficient sample size to evaluate the impact in various gender and ethnic subgroups. Thus, we propose to randomize 150 DWI offenders and 150 CFMs to each arm of the trial.

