### Outcome Analysis Plan

The trial is intended to evaluate the following hypotheses:

**H1:** First-time DWI offenders in the intervention group (*B-SMART mobile web app*) will have significantly fewer IID lockout events than participants in the control group (UC information condition).

**H2:** Lower rates of IID lockout events will be mediated by improvements in Family Functioning, Family Communication, and Shared Positive Family Events in the intervention (*B-SMART mobile web app*) condition compared to the UC information condition.

We will also analyze the moderation of the effect of *B-SMART* by demographics and mediation of IID lockout events by *B-SMART* use in the intervention group.

Three levels of analysis are planned: (1) hypothesis testing using Poisson regression testing the differences in lockout events between the two intervention groups, (2) analysis of possible covariates (e.g., sex, ethnicity, and age of DWI offenders and CFMs), added to the Poisson regression and (3) other exploratory analyses.

**Preliminary Analysis of Baseline Data.** Descriptive data at baseline, with comparisons by treatment group, will be examined to check distributional characteristics and assess any concerns for imbalances that might be considered as covariates in analyses. The potential meaning of non-normality will be examined, i.e., excessive skewness potentially identifying key subgroups. These analyses will be at the level of the individual DWI offenders and CFMs responses and be conducted within 3 months of completion of recruitment. If there is excessive skewness on the IID lockout rates, negative binomial regression will be used.

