**Planned Analysis for Hypothesis 1.** The second major analysis will focus on impact of the *B-SMART mobile web app* on primary (IID lockout events) and secondary (DWI offender's alcohol consumption) outcomes and be completed within 1 month of the end of the posttest data collection in Year 2. The effect of *B-SMART* on IID lockout events in Hypothesis 1 will be tested primarily using PROC GENMOD with a Poisson link via SAS Version 9.4, which includes capabilities to test these Poisson models with missing data, account for the temporal design, and include information by participant. Participants will be treated as a random effect and treatment as a fixed effect, at  $p=0.05$  (2-sided). Analyses of primary outcomes will not be released before completion of the intervention. Since CFM and DWI offender can be clustered within the same family, hierarchical models with participants nested within families will be considered.

The secondary outcome of quantity and frequency of alcohol consumption by DWI offenders will be compared in several ways. Quantity and frequency will be evaluated using Poisson models, as well as a composite variable based on total alcohol consumption (the product of the two variables), using negative binomial regression models, unless a Poisson model is sufficient.

Since date of IID lockout events will be collected and alcohol consumption is measured at all three assessments, we will examine the time by treatment interaction in the analyses of Hypothesis 1 to assess the

question of the durability of the effects of B-SMART over time. For example, we will evaluate time to first lockout using a Kaplan Meier approach and the times to subsequent lockouts.

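### The plan names Poisson models for Form 90 drinking quantity and frequency and states no handling of overdispersion, so their nominal 5% tests may reject too often

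*Combined protocol and SAP*

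**What the plan says.** Alcohol use by the offender is the only outcome labelled secondary (protocol, Section 4.3). Protocol 3C.7.2 describes the instrument: "The Form 90 measures produce detailed quantity and frequency measure of alcohol use for the first-time offender". It is given at baseline, 3 months and 9 months. No mean, SD, share of abstainers or recall window is stated.

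The method is in the SAP under Planned Analysis for Hypothesis 1, with the same text in protocol 3C.8.2 and in the statistical design attachment to Section 4.4. For the two components: "Quantity and frequency will be evaluated using Poisson models". The sentence then turns to a "composite variable based on total alcohol consumption (the product of the two variables), using negative binomial regression models, unless a Poisson model is sufficient".

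Four other statements bear on it:

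- The fallback under Preliminary Analysis of Baseline Data: "If there is excessive skewness on the IID lockout rates, negative binomial regression will be used". It names lockouts only.
- The lockout effect "will be tested primarily using PROC GENMOD with a Poisson link via SAS Version 9.4".
- The next sentence: "Participants will be treated as a random effect and treatment as a fixed effect". It is not repeated for drinking.
- Distributions are to be examined at baseline (same preliminary section), and distributional assumptions assessed when data collection ends (Data and Safety Monitoring Plan). Neither place says what will be done if the drinking data fail the check.

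**The concern.** The plan allows for extra variation in the lockout counts and in the drinking composite, but not, as written, in the two components of that composite. A Poisson model has no free variance parameter. If offenders differ in how often or how much they drink, beyond Poisson sampling variation, the model-based standard error is too small. The confidence interval is then too narrow, and the test rejects a true null more often than 5%.

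Some such difference between offenders is likely on the plan's own evidence. The Phase I development interviews (protocol 3C.1.3) separate families whose relative had drinking under control from those whose relative was still a problem drinker. That supports the direction of the error but gives no size.

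At stake is a claim that the app reduces drinking. The plan also uses the drinking data, since "alcohol consumption is measured at all three assessments", to judge whether effects last.

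**Working it through.** **The plan's own figure.** No power or error figure is given for drinking. The stated sample size is for lockouts: "Assuming a Type I error of 0.05 (2-sided), 90% power, sample size is only 27 DWI offenders per group". With 4 and 2.4 events over 9 months, n = (1.96 + 1.2816)² × (1/4 + 1/2.4) / ln(0.6)² = 10.507 × 0.6667 / 0.2609 = 26.8, so 27. This reproduces the plan's figure and shows that its calculation uses Poisson variance with no allowance for extra spread.

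**Inputs.** From the documents: two-sided 5% test; 150 offenders per arm and 15% attrition, so 150 × 0.85 = 127.5, taken as 127 per arm. Assumed, because the documents are silent: the variance-to-mean ratio φ, a 90-day window, and the means and SDs below.

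**Formula.** If the variance is φ times the mean, the Poisson standard error is 1/√φ of its true size, and the 5% Wald test has size 2Φ(−1.96/√φ).

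| φ (assumed) | Poisson SE / true SE | True size of 5% test |
|---|---|---|
| 1 | 1.00 | 5% |
| 1.5 | 0.82 | 11% |
| 2 | 0.71 | 17% |
| 3 | 0.58 | 26% |
| 5 | 0.45 | 38% |
| 10 | 0.32 | 54% |

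**Frequency.** Take drinking days as beta-binomial with N = 90 and mean 18 days (p = 0.2). Then φ = (1 − p)[1 + (N − 1)ρ] = 0.8(1 + 89ρ), where ρ is the intraclass correlation.

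- ρ = 0 gives φ = 0.8. The cap on days lowers the variance, so with identical offenders the Poisson test would be conservative.
- Break-even, φ = 1, needs 89ρ = 0.25, so ρ = 0.003, an SD of √18 = 4.2 days.
- ρ = 0.05, 0.10 and 0.30 give φ = 4.4, 7.9 and 22.

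Null simulations with 127 per arm gave these false-positive rates at mean 18:

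| SD (days) | False positives |
|---|---|
| 5.2 | 11% |
| 6.3 | 19% |
| 8.9 | 34% |
| 11.9 | 48% |
| 20 | 68% |

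Other assumed means, from 5 to 30 days with SD 5 to 23, gave 38% to 70%.

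**Quantity.** Drinks per drinking day, simulated as negative binomial with and without excess zeros:

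| Assumed spread | False positives |
|---|---|
| mean 3, SD 2 | 9% |
| mean 4, SD 3 | 18% |
| mean 5, SD 4 | 29% |
| mean 6, SD 5 | 35% |
| 30% zeros, others mean 4, SD 3 | 27% |
| 50% zeros, others mean 5, SD 4 | 42% |

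**Remedies, same kind of null data.** Robust standard errors gave 3.9% to 6.1% and scaled Poisson 3.8% to 5.9% (1,500 trials per setting). In two settings with counts at two visits (400 trials each), negative binomial on one visit gave 5.8% in both, and Poisson GEE with robust standard errors on both visits gave 5.3% and 6.5%. Ignoring the clustering and pooling the two visits gave 71% and 38%. When the data were truly Poisson (mean 10), ordinary and robust standard errors gave 4.7% and 5.1%, so the remedy did not distort the test where it was not needed.

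**The case against.** The strongest reply is that the participant effect already deals with this. The Hypothesis 1 section opens by covering primary and secondary outcomes together. Repeated drinking measurements suit a participant effect at least as well as one cumulative lockout count does. If it is fitted to drinking, for instance as GEE with robust standard errors, most of the inflation goes. This stands as a possibility. But the sentence follows directly on the lockout model and is not repeated for drinking, so the text does not settle it.

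Second, the negative binomial clause might be meant for all three drinking variables. The sentence is more naturally read as assigning it to the composite. Even on the wider reading, no criterion says when Poisson is good enough, so the choice could be made after seeing results.

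Third, distribution checks are planned. That is true, but no action for drinking is tied to them.

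Fourth, the documents contain no dispersion figure. This stands in full. A reader might infer that both tests are bound to have error rates many times 5%. The documents do not support that: at the tightest spread tried, quantity is at about 9%, under twice nominal. A reader might also think that the limit on drinking days adds to the problem. It works the other way, as φ = 0.8 at ρ = 0 shows.

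**Conclusion.** The point holds in conditional form. The stated method for quantity and frequency has no overdispersion handling, and following it as written gives standard errors that are too small whenever the variance exceeds the mean. The size rests on assumed spreads: about 17%, 38% and 54% at φ of 2, 5 and 10, and across the simulations about 11% to 70% for frequency and 9% to 42% for quantity. It further assumes that neither the participant effect nor the negative binomial clause is meant for these two variables, which is the likelier reading but not the only one.

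The reach is limited. Hypotheses 1 and 2 both concern lockouts, and the primary lockout test is not affected. The change should be made before the drinking data are analysed, but the trial does not depend on it.

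**What to change.** Amend the secondary-outcome paragraph in the SAP, and the same text in protocol 3C.8.2 and the Section 4.4 attachment, to say that:

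- quantity, frequency and the composite are each analysed by a method that allows for overdispersion: negative binomial regression, or a log-linear model with sandwich standard errors clustered on offender across the 3- and 9-month visits, the choice being fixed in advance;
- participant-level clustering applies to the drinking outcomes;
- the baseline Form 90 value, already collected, is a covariate;
- for frequency, log window length is an offset only if windows differ between participants.

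The essential part is the variance method; baseline adjustment is an inexpensive addition. The cost is SAP wording and wider, correct confidence intervals. No new data or participants are needed, and if the variance turns out close to the mean the results will hardly change.

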### 3C.6. Randomized Trial Evaluating *B-SMART* (Specific Aim 4; Months 8-24)

**3C.6.1. Experimental Design.** The *B-SMART mobile web app* will be evaluated in a randomized pretest-posttest controlled design. In months 6-11, first time DWI offenders and CFMs will be recruited for participation in the trial. First-time DWI offenders and their CFMs will be randomized together to the intervention (*B-SMART*)

(n=150) or a usual and customary (UC) IID information condition comparison group (n=150) following baseline assessment. Assessment via web-based surveys will be conducted with the DWI offenders and CFMs at baseline, 3-month follow-up, and 9-month follow-up

post randomization. Also, information on frequency of alcohol-positive IID tests (termed “lockout events”) will be acquired by the project from the Santa Fe County and Municipal DWI Program at the 9-month assessment point (posttest only) for each DWI offender. Thus, the proposed efficacy trial (see **Figure 5**) will be a 2 (level of treatment – app intervention vs. UC information) x 3 (level of time – baseline vs. 3-month follow-up vs. 9-month follow-up) mixed factorial design. Baseline and follow-up data collection will be conducted via online surveys and a customized web portal and include DWI offender and CFM alcohol frequency and use measures and measures of family communication and functioning (see 3C.7). Participants will fill out a locator form with contact information and collateral contact information to locate them for assessment at the 3-month and 9-month follow-ups. We have employed these locator procedures in prior trials, keeping average loss across 9 months at 15%-20%. Cumulative IID lockout event data will be collected for all DWI offenders from the Santa Fe County DWI Program at the 9-month assessment point.

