**Planned Analysis for Hypothesis 1.** The second major analysis will focus on impact of the *B-SMART mobile web app* on primary (IID lockout events) and secondary (DWI offender's alcohol consumption) outcomes, and be completed within 1 month of the end of the posttest data collection in Year 2. The effect of *B-SMART* on IID lockout events in Hypothesis 1 will be tested primarily using PROC GENMOD with a Poisson link via SAS Version 9.4, which includes capabilities to test these Poisson models with missing data, account for the temporal design, and include information by participant. Participants will be treated as a random effect and treatment as a fixed effect, at  $p=0.05$  (2-sided). Analyses of primary outcomes will not be released before completion of the intervention. Since CFM and DWI offender can be clustered within the same family, hierarchical models with participants nested within families will be considered.

The secondary outcome of quantity and frequency of alcohol consumption by DWI offenders will be compared in several ways. Quantity and frequency will be evaluated using Poisson models, as well as a

composite variable based on total alcohol consumption (the product of the two variables), using negative binomial regression models, unless a Poisson model is sufficient.

Since date of IID lockout events will be collected and alcohol consumption is measured at all three assessments, we will examine the time by treatment interaction in the analyses of Hypothesis 1 to assess the question of the durability of the effects of B-SMART over time. For example, we will evaluate time to first lockout using a Kaplan Meier approach and the times to subsequent lockouts.

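### The analysis of offender drinking, the only secondary outcome, does not specify adjustment for the baseline Form 90 value that the trial already collects

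*Combined protocol and SAP*

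**What the plan says.** Section 3C.7.2 sets the measurement schedule: "Alcohol use by the DWI offender, a secondary outcome, will be assessed at baseline, 3-month follow-up, and 9-month follow-up". Section 4.3 lists alcohol use as the only secondary outcome. Section 3C.6.1 places randomisation after the baseline assessment, so almost every randomised offender should have a pre-randomisation Form 90 value.

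The arm comparison is described under Planned Analysis for Hypothesis 1 in the SAP, with the same text in 3C.8.2 and 4.4: "Quantity and frequency will be evaluated using Poisson models, as well as a composite variable based on total alcohol consumption". The composite is the product of quantity and frequency and gets a negative binomial model unless a Poisson model is adequate. The text names distributions but lists no model terms.

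Three other passages bear on baseline or on covariates:

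- Section 3C.6.1 describes a two-arm design crossed with "3 (level of time – baseline vs. 3-month follow-up vs. 9-month follow-up) mixed factorial design". The SAP adds a time-by-treatment interaction, offered to assess whether effects last.
- The Outcome Analysis Plan has a covariate step for the Poisson regression of lockout events. Its examples are demographic (sex, ethnicity, age) and are given only as examples.
- Preliminary Analysis of Baseline Data says that baseline data will be compared by arm and that imbalances may be considered as covariates. It gives no rule and names no variable.

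**The concern.** An offender's drinking before randomisation is likely to be the best available predictor of that offender's drinking at follow-up. Adjusting for it removes the predictable part of the between-person variation and so narrows the confidence interval for the treatment effect. If the text is followed as written, the analyst may omit this, or may decide after seeing the data.

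Two things are at stake. The first is precision on an outcome for which no power is stated and which, unlike lockouts, is not confined to the interlock-fitted vehicle. The second is chance imbalance. Suppose the arms differ at baseline by D standard deviations. With equal variances and correlation rho, a follow-up-only estimate carries rho x D of that difference, and a change-type estimate over-corrects by (1 - rho) x D. At rho = 0.5 each is off by half of D. The baseline-adjusted estimate removes the linear part of the imbalance.

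**Working it through.** **The plan's own figures.** These concern lockouts only. Inputs are "We have assumed 4 interlocks over 9 months in the control arm or a rate of 0.44 per month for each DWI offender" and "The null hypothesis is that the ratio of these two rates is 1.0 versus 0.6". For two Poisson means, n per group = (1.960 + 1.282)^2 x (1/m1 + 1/m2) / [ln(m1/m2)]^2, and (1.960 + 1.282)^2 = 10.507.

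- Ratio 0.6 (means 4 and 2.4): 10.507 x 0.6667 / 0.2609 = 26.8, so 27. This matches "Assuming a Type I error of 0.05 (2-sided), 90% power, sample size is only 27 DWI offenders per group".
- Ratio 0.8 (means 4 and 3.2): 10.507 x 0.5625 / 0.04979 = 118.7, so 119. This matches "a sample size of 119 DWI offenders per group will allow for 90% power with a comparison of 0.44 to 0.36" when the unrounded ratio of 0.8 is used; the printed 0.44 and 0.36 would give 147.
- Attrition of 15%: 119 / 0.85 = 140, which 150 per arm covers. About 127 per arm remain (150 x 0.85 = 127.5).

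No corresponding calculation exists for drinking. Starting power and rho below are therefore assumptions.

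**Variance of the arm comparison at one follow-up**, in units of the follow-up-only variance, with equal variance at both occasions:

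- follow-up only: 1
- change from baseline (the type of contrast a time-by-treatment interaction tests): 2(1 - rho)
- adjusted for baseline: 1 - rho^2 = (1 - rho)(1 + rho)

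Because 1 + rho is below 2 whenever rho is below 1, the adjusted variance is always smaller than the change variance. It is never larger than the follow-up-only variance.

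**Power.** Let d = 1.960 + z(power of the follow-up-only test). Then adjusted power = Phi(d / sqrt(1 - rho^2) - 1.960) and change-type power = Phi(d / sqrt(2(1 - rho)) - 1.960). For 80%, d = 2.802.

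At rho = 0.5: 2.802 / sqrt(0.75) = 3.235, and Phi(1.275) = 89.9%. The change-type variance is 2 x 0.5 = 1, so its power stays at 80.0%.

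| rho | follow-up only | change-type | adjusted | gain over follow-up only | gain over change-type |
|---|---|---|---|---|---|
| 0.3 | 80% | 65.8% | 83.6% | 3.6 | 17.7 |
| 0.4 | 80% | 72.5% | 86.4% | 6.4 | 13.9 |
| 0.5 | 80% | 80.0% | 89.9% | 9.9 | 9.9 |
| 0.6 | 80% | 87.9% | 93.8% | 13.8 | 5.9 |
| 0.7 | 80% | 95.1% | 97.5% | 17.5 | 2.4 |

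From 90% follow-up-only power (d = 3.242), adjusted power is 92.5% at rho 0.3, 96.3% at 0.5 and 99.5% at 0.7. The gains are 2.5, 6.3 and 9.5 points.

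**Check on counts.** The formulas are for normal outcomes, so counts were simulated with 127 offenders per arm. Assumptions were a mean of 20, between-person log-SD of 0.8, a rate ratio of 0.73, a negative binomial model with robust standard errors, and 1,500 replicates. The change-type column is a linear model of log change.

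| observed log-scale correlation | follow-up only | change-type | adjusted |
|---|---|---|---|
| 0.29 | 74.7% | 67.7% | 80.5% |
| 0.47 | 75.9% | 80.3% | 88.5% |
| 0.65 | 73.7% | 94.7% | 96.8% |

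The pattern and order of size agree with the formulas. Every simulation input except the number per arm is assumed.

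**The case against.** The strongest reply is that the text is silent rather than wrong. It lists no terms for the drinking models, so it cannot be read as a decision to fit treatment alone. The covariate examples are only examples. The imbalance provision is not limited to lockouts and could bring baseline drinking in. The study-team section promises a more detailed analysis plan from the Analysis Subcommittee. An unadjusted randomised comparison is also valid, so the issue is efficiency on a secondary outcome with no power target.

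Most of this stands, and it limits the claim. A reader might infer that the plan excludes baseline drinking or allows only demographic covariates; the documents support neither. A reader might also take 10 points as the cost. That figure needs both rho = 0.5 and 80% starting power, and neither is in the documents. Nor is the gain always large: against a change-type contrast it falls below 5 points above a rho of about 0.62. Finally, one could suppose that the test is a treatment main effect averaged over all three occasions, including the one before treatment, which would dilute the effect badly. No passage proposes that test.

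The reply does not remove the gap. The imbalance provision depends on looking at the data, and it brings no precision gain when the arms happen to be balanced. The interaction is offered to study durability and, read as a change contrast, is less efficient than adjustment at every rho below 1. A future analysis plan is a place to put the sentence, not evidence that it exists.

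**Conclusion.** The point holds as one of specification. The plan collects baseline Form 90 drinking and does not say that the arm comparison of drinking will be adjusted for it. Taking the follow-up-only test at an assumed 80% power, adjustment is worth about 4, 10 and 18 points at rho 0.3, 0.5 and 0.7. The range is about 2 to 10 points if that test has 90% power. Against a change-type contrast on the 80% calibration, the gains run the other way: about 18, 10 and 2 points.

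These sizes rest on assumed correlations and starting powers, equal variances at baseline and follow-up, and normal theory that only approximates the Poisson and negative binomial models. The direction does not depend on the choice of rho: within that framework, adjustment is at least as efficient as either alternative. The finding does not touch the validity of an unadjusted comparison or the lockout analysis.

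**What to change.** In the secondary-outcome paragraph of the SAP, and in the matching text of 3C.8.2 and 4.4, state the following:

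- The response is each drinking variable (quantity, frequency, composite) at months 3 and 9. Baseline is not an outcome occasion.
- Fixed terms are treatment, visit and treatment-by-visit.
- The offender's own baseline value of the same variable, as log(x + 1), is a pre-specified covariate whether or not the arms look balanced.
- The treatment ratio is reported at each follow-up.

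The cost is a short wording change before unblinding, with no new data, visits or participants. The model uses one more degree of freedom. A simple rule is needed for offenders with no baseline value, such as a missing indicator or simple imputation; few are expected, because randomisation follows the baseline assessment.

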**3C.8.2. Planned Analysis for Hypothesis 1.** The second major analysis will focus on impact of the *B-SMART mobile web app* on primary (IID lockout events) and secondary (DWI offender's alcohol consumption) outcomes, and be completed within 1 month of the end of the posttest data collection in Year 2. The effect of *B-SMART* on IID lockout events in Hypothesis 1 will be tested primarily using PROC GENMOD with a Poisson link via SAS Version 9.4, which includes capabilities to test these Poisson models with missing data, account for the temporal design, and include information by participant. Participants will be treated as a random effect and treatment as a fixed effect, at  $p=0.05$  (2-sided). Analyses of primary outcomes will not be released before completion of the intervention. Since CFM and DWI offender can be clustered within the same family, hierarchical models with participants nested within families will be considered.

The secondary outcome of quantity and frequency of alcohol consumption by DWI offenders will be compared in several ways. Quantity and frequency will be evaluated using Poisson models, as well as a composite variable based on total alcohol consumption (the product of the two variables), using negative binomial regression models, unless a Poisson model is sufficient.

Since date of IID lockout events will be collected and alcohol consumption is measured at all three assessments, we will examine the time by treatment interaction in the analyses of Hypothesis 1 to assess the question of the durability of the effects of *B-SMART* over time. For example, we will evaluate time to first lockout using a Kaplan Meier approach and the times to subsequent lockouts.

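### For the drinking outcome, a time-by-treatment interaction that includes baseline cannot tell an effect kept to month 9 from one lost by then, so it does not assess durability

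*Combined protocol and SAP*

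**What the plan says.** The SAP (Planned Analysis for Hypothesis 1, with the same text in protocol section 3C.8.2 and in the Statistical Design and Power attachment, 4.4) gives two reasons for its durability analysis. One is that lockout dates will be collected. The other is that "alcohol consumption is measured at all three assessments, we will examine the time by treatment interaction in the analyses of Hypothesis 1". The purpose is to address the "question of the durability of the effects of B-SMART over time". The worked example that follows, Kaplan-Meier for time to first lockout and then times to later lockouts, concerns lockouts only.

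Section 3C.6.1 describes the trial as a factorial in which time has the levels "level of time – baseline vs. 3-month follow-up vs. 9-month follow-up", with randomisation "following baseline assessment". Section 3C.7.2 confirms the schedule for drinking: "Alcohol use by the DWI offender, a secondary outcome, will be assessed at baseline, 3-month follow-up, and 9-month follow-up". On the model, the SAP says that "Quantity and frequency will be evaluated using Poisson models", with negative binomial regression for the composite unless Poisson is sufficient.

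No section limits the interaction to post-baseline visits, names a contrast between months 3 and 9, makes baseline drinking a covariate, or says how a significant or non-significant interaction is to be read.

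**The concern.** Durability asks whether an effect present at month 3 is still there at month 9. Once baseline is a level of time, the interaction asks something else: whether the arm difference varies anywhere across the three assessments. Any post-baseline effect makes it vary, because the difference starts at zero. The test is then mainly a test that the app changed drinking at some time, whatever happened between months 3 and 9.

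Drinking is the only outcome that section 4.3 lists as secondary, and lasting change is the purpose of the programme. If no contrast is fixed in advance, the comparison that really addresses durability will be picked after the data are seen, or the overall p-value will be asked to carry a meaning that it does not have.

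**Working it through.** **Inputs from the documents.** 150 offenders per arm and 15% attrition (Sample Size Determination): 150 × 0.85 = 127.5, taken as 127. Two-sided alpha 0.05. Drinking measured at baseline, month 3 and month 9.

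**Inputs assumed.** The documents give no drinking SD, effect size or within-person correlation. I use effects of d = 0.2 to 0.5 SD on a normal scale. Correlations are either 0.5 throughout, or 0.5 (baseline to 3), 0.4 (baseline to 9) and 0.6 (3 to 9).

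**The plan's own figures.** The lockout sample sizes reproduce with n = (1.960 + 1.282)² × (1/m1 + 1/m2) / [ln(m2/m1)]². Means of 4 and 2.4 give 26.8, so 27. Means of 4 and 3.2 give 118.7, so 119. They are not in dispute. No power is stated for the interaction.

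**Step 1: the overall interaction (2 df), equal correlation.** The noncentrality is n / [2(1 − rho)] × Σ(d_t − mean d)².
- Kept, (0, d, d): the mean is 2d/3, and the squared deviations are (4 + 1 + 1)d²/9 = 2d²/3.
- Lost, (0, d, 0): the mean is d/3, and the squared deviations are (1 + 4 + 1)d²/9 = 2d²/3.

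The two are identical for every d. With n = 127 and rho = 0.5 the noncentrality is 127 × 2d²/3:

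| d (SD) | Noncentrality | Power if kept | Power if lost |
|---|---|---|---|
| 0.2 | 3.39 | 36% | 36% |
| 0.3 | 7.62 | 70% | 70% |
| 0.4 | 13.55 | 92% | 92% |
| 0.5 | 21.17 | 99% | 99% |

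**Step 2: unequal correlation.** With 0.5/0.4/0.6 and d = 0.4, the noncentrality is 11.45 if kept and 17.17 if lost, so power is 87% and 97%. The lost effect is then the more likely to give significance.

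**Step 3: counts.** Overdispersed Poisson data were simulated at 127 per arm, with robust variance and 2000 runs per pattern. The three-level interaction was significant as follows: rate ratio 0.8, 37% kept and 38% lost; 0.7, 71% and 70%; 0.6, 94% and 94%. The test was slightly liberal (8% under the null).

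**Step 4: month 9 against month 3 (1 df).** The noncentrality is n(d9 − d3)² / [4(1− rho39)], where rho39 is the month-3-to-month-9 correlation.
- Kept: 0, so 5%.
- Lost, d = 0.4: 127 × 0.16 / 2 = 10.16, so 89% at rho39 = 0.5; 127 × 0.16 / 1.6 = 12.7, so 95% at rho39 = 0.6.
- Lost, d = 0.2, rho39 = 0.5: 127 × 0.04 / 2 = 2.54, so 36%.

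In the count simulation at rate ratio 0.7 this contrast was significant in 6% of trials if kept and 66% if lost (7% under the null).

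**Step 5: baseline as covariate.** For the month-9 arm effect, z = d / √[2(1 − r²)/n], with r the baseline-to-month-9 correlation. At d = 0.4: unadjusted, 3.19, power 89%; r = 0.4, 3.48, power 94%; r = 0.5, 3.68, power 96%.

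**The case against.** The plan says only that it will examine the interaction. It does not name a 2-df test, tie durability to a p-value or give a reading rule, and an analyst examining an interaction would normally look at arm differences by visit. That stands. A reader might infer that the plan contains a rule that will report the wrong answer; the text does not go that far. The criticism that holds is that the analysis it names cannot answer its question and that no contrast that could is specified.

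Baseline as a level of time in the drinking model is an inference, from joining the phrase about all three assessments to the factorial description in section 3C.6.1. If time were instead a linear trend in months, a lost effect would be significant in only 11% of trials and a kept one in 80% (d = 0.4, rho = 0.5, n = 127). The documents describe levels, not a slope, so this is the less likely reading; if it is intended, the plan should say so.

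The sentence sits under Hypothesis 1, which concerns lockouts, and drinking has its own planned arm comparisons. Both points are correct, and they limit the reach. Nor is baseline in a longitudinal model wrong in itself: with the arms constrained equal at baseline, such a model is valid.

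**Conclusion.** The point holds for the secondary drinking outcome. With baseline among the time levels, kept and lost effects are both departures from the null, with equal power under equal correlation and similar power otherwise. The overall interaction cannot show durability. A non-significant result may be no effect or a missed effect; it is not evidence of a constant one.

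The equality in step 1 is algebra and needs only equal variances and correlations and a zero expected difference at baseline. The power percentages rest on assumed effects and correlations.

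Two stronger readings are not supported. A reader might infer that both patterns will make the test significant; at 0.2 SD each does so in only 36% of trials. A reader might also extend the problem to the primary outcome; section 3C.6.1 says that lockouts are acquired at posttest only, so they have no baseline level. The change is worth making because it replaces an analysis that cannot answer its question with one that can, from data already planned.

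**What to change.** In the durability sentence (SAP, section 3C.8.2 and the copy in 4.4), treat the Form 90 drinking outcomes separately from lockouts:

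- Model months 3 and 9 with baseline drinking as a covariate and terms for arm, visit and arm by visit, keeping the planned Poisson or negative binomial form. A longitudinal model with the arms constrained equal at baseline is an acceptable alternative.
- Name the month-9 arm effect, with its 95% CI, as the durability estimate.
- Test fading by the single month-9-versus-month-3 arm contrast, and state that a non-significant contrast does not by itself prove durability.

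Leave the 2 × 3 description in section 3C.6.1 as it is. It correctly describes data collection, and the mediation analysis needs the baseline-to-3-month change in the family measures.

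The cost is protocol and SAP wording; no new data are needed. Under the step 5 assumptions, using baseline drinking as a covariate also raises month-9 power from 89% to about 94–96%.
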